9.0 Study Drug Exposure and Compliance

The summaries described below will be performed for the set of all subjects and for the geographic region of China.

9.1 Exposure

The duration of exposure to study drug will be summarized separately for the DB Treatment Period (for each treatment arm and overall in the safety population) and the OL Treatment Period (for the OL population). For each of the treatment periods, duration of

exposure is defined for each subject as the last study drug dose date minus the first study drug dose date plus 1 day.

Descriptive statistics (mean, standard deviation, median, minimum, and maximum) will be presented for exposure during each treatment period. Study drug duration will also be summarized with frequencies and percentages using the following categories:

- 1 to 15 days
- 16 to 30 days
- 31 to 45 days
- 46 to 60 days
- 61 to 75 days
- 76 to 90 days
- 91 to 105 days
- > 105 days

In addition, the number and percentage of subjects during the DB Treatment Period (for each treatment arm and overall in the safety population) and the OL Treatment Period (for the OL population) with a study drug duration of ≥ 52 days or ≥ 105 days will be summarized.

9.2 Compliance

During the DB and OL Treatment Periods, at each Study Drug Dispensation visit the number of tablets dispensed is automatically calculated according to the number of bottles dispensed, and at each Study Drug Accountability visit (starting with the Week 4 visit), the total number of tablets returned is recorded. The compliance for each study drug (ABT-493/ABT-530 or matching placebo) during the DB Treatment Period will be calculated as the percentage of tablets taken relative to the total tablets expected to be taken. The total number of tablets expected to be taken will be equal to the total number of tablets that should have been taken per the protocol for the duration that the subject was in the DB Treatment Period (date of last dose of study drug – date of first dose of study

drug + 1). DB study drug interruptions recorded on the eCRF will not be subtracted from the duration.

A subject is considered to be compliant if the percentage is between 80% and 120%. Compliance will be calculated for each subject and summarized with the mean, median, standard deviation, minimum, and maximum by treatment arm. The percentage of compliant subjects will be summarized for each study drug and each treatment arm, based on data as observed. An additional summary of the percentage of compliant subjects will be provided where subjects who are missing study drug accountability records will be imputed as non-compliant.

The summaries described above will be performed on the ITT population; similar summaries of the compliance for the active study drug (ABT-493/ABT-530) during the OL Treatment Period will be provided for the OL population.

10.0 Efficacy Analysis

10.1 General Considerations

General Considerations

Treatment effects will be evaluated based on a 2-sided significance level of 0.050 (when rounded to three decimal places), and all efficacy analyses will be performed on the ITT population randomized to Arm A, unless otherwise specified.

Missing data will be imputed as described in Section 6.3 for analyses of the HCV RNA endpoints of SVR.

Plasma HCV RNA levels will be determined for each sample collected by the central laboratory using the Roche COBAS[®] AmpliPrep/COBAS[®] TaqMan[®] HCV Quantitative Test, v2.0. The lower limit of detection (LLOD) and lower limit of quantification (LLOQ) for this assay (regardless of genotype) are both 15 IU/mL.

HCV RNA results that are detectable but not quantifiable are reported as "< 15 IU/ML HCV RNA DETECTED" and those that are undetectable are reported as "HCV RNA NOT DETECTED" in the database.

The notation "HCV RNA < LLOQ" is used to represent all HCV RNA values < 15 IU/mL, including values reported as "HCV RNA NOT DETECTED" or "< 15 IU/ML HCV RNA DETECTED." HCV RNA \geq LLOQ are all quantifiable values of 15 IU/mL or greater.

IL28B rs12979860 will be resulted as C/C, C/T, or T/T by the central laboratory.

Definitions for Efficacy Endpoints

A confirmed quantifiable value during treatment is defined as any two consecutive HCV RNA measurements \geq LLOQ (or 100 IU/mL for **Breakthrough**), either both during treatment or at the final treatment measurement and the next consecutive post-treatment measurement. A confirmed quantifiable post-treatment value is defined as any two consecutive post-treatment HCV RNA measurements \geq LLOQ.

Breakthrough = confirmed HCV RNA \geq 100 IU/mL after HCV RNA < LLOQ during the Treatment Period; or confirmed increase from nadir in HCV RNA (two consecutive HCV RNA measurements > 1 log₁₀ IU/mL above nadir) at any time point during the Treatment Period. A single breakthrough value (\geq 100 IU/mL or > 1 log₁₀ above nadir) followed by lost to follow-up also will be considered a breakthrough (i.e., will not require confirmation).

EOT failure = HCV RNA \geq LLOQ at end of treatment with at least 6 weeks of treatment, where the HCV RNA value must be collected on or after Study Drug Day 36 and study drug duration \geq 36 days.

On-treatment HCV virologic failure = **Breakthrough** or **EOT failure**; if a subject meets both definitions of **Breakthrough** and **EOT failure**, he or she will be categorized as **Breakthrough** only.

SVR₄ = HCV RNA < LLOQ in the SVR₄ window (4 weeks after the last actual dose of active study drug) without any confirmed quantifiable (\geq LLOQ) post-treatment value before or during that SVR window.

SVR₁₂ = HCV RNA < LLOQ in the SVR₁₂ window (12 weeks after the last actual dose of active study drug) without any confirmed quantifiable (\geq LLOQ) post-treatment value before or during that SVR window.

SVR₂₄ = HCV RNA < LLOQ in the SVR₂₄ window (24 weeks after the last actual dose of active study drug) without any confirmed quantifiable (\geq LLOQ) post-treatment value before or during that SVR window.

Relapse₁₂ = confirmed HCV RNA \geq LLOQ between end of treatment and 12 weeks after last actual dose of active study drug (up to and including the SVR₁₂ assessment time point) for a subject with HCV RNA < LLOQ at Final Treatment Visit who completed treatment and has post-treatment HCV RNA data available, excluding reinfection as described below.

Relapse₂₄ = confirmed HCV RNA \geq LLOQ within the SVR₂₄ window for a subject who achieved SVR₁₂ and has HCV RNA data available in the SVR₂₄ window, excluding reinfection.

Relapse_{overall} = confirmed HCV RNA \geq LLOQ between end of treatment and up to and including the last HCV RNA measurement collected in the PT Period for a subject with HCV RNA < LLOQ at Final Treatment Visit who completed treatment and has post treatment HCV RNA data available, excluding reinfection.

Only subjects who have at least one post-treatment HCV RNA value will be included in analyses of relapse. For the analyses of relapse, completion of treatment is defined as a study drug duration of 52 days or greater for subjects assigned to 8 weeks of treatment and 105 days or greater for subjects assigned to 16 weeks of treatment. If the last available post-treatment value is \geq LLOQ, then the subject will be considered a relapse (i.e., will not require confirmation).

HCV reinfection is defined as confirmed HCV RNA \geq LLOQ after the end of active treatment in a subject who had HCV RNA $<$ LLOQ at Final Treatment Visit, along with the post treatment detection of a different HCV genotype, subtype, or clade compared with baseline, as determined by phylogenetic analysis of the NS3 or NS5A, and/or NS5B gene sequences. Reinfection in the case of the same HCV subtype is defined as a clade switch, as indicated by the lack of clustering between the baseline and post-treatment sequences by phylogenetic analysis. If phylogenetic analysis is not possible due to technical difficulties, HCV reinfection may be determined with a confirmed HCV genotype or subgenotype switch by the Versant HCV Genotype Inno-LiPA Assay v2.0 or Sanger assay.

Post-treatment relapse is defined as described earlier (**Relapse₁₂**, **Relapse₂₄**, **Relapse_{overall}**), and no genotype, subtype, or clade switch compared with baseline as determined by phylogenetic analysis of the NS3 or NS5A gene sequences. If phylogenetic analysis is not possible due to technical difficulties, the subject will be defined as having a post-treatment relapse unless an HCV genotype or subgenotype switch is confirmed by the Versant HCV Genotype Inno-LiPA Assay v2.0 or Sanger assay.

Reasons for SVR₁₂ Non-Response

Subjects who do not achieve SVR₁₂ (SVR₁₂ non-responders) will be categorized as having:

1. On-treatment HCV virologic failure (see **On-treatment HCV virologic failure** definition; if a subject meets both definitions of **Breakthrough** and **EOT failure**, he or she will be categorized as **Breakthrough** only);
2. Relapse₁₂;
3. Prematurely discontinued study drug with no on-treatment virologic failure (defined as any SVR₁₂ non-responder who prematurely discontinued study drug [study drug duration $<$ 52 days for subjects assigned to 8 weeks of treatment, and

- < 105 days for subjects assigned to 16 weeks of treatment] and did not meet the **On-treatment HCV virologic failure** definition);
4. HCV reinfection (see definition described earlier);
 5. Missing follow-up data in the SVR₁₂ window (defined as any subject who completed study drug without data in the SVR₁₂ window after applying the imputation rules and not meeting the definitions of [1], [2], [3], or [4]);
 6. Other (defined as any SVR₁₂ non-responder not meeting the definitions of [1] – [5]).

Reasons for SVR₂₄ Non-Response

Subjects who do not achieve SVR₂₄ (SVR₂₄ non-responders) will be categorized as having:

1. On-treatment HCV virologic failure (see **On-treatment HCV virologic failure** definition, if a subject meets both definitions of **Breakthrough** and **EOT failure**, he or she will be categorized as **Breakthrough** only);
2. Relapse₁₂;
3. Relapse₂₄;
4. Prematurely discontinued study drug with no on-treatment virologic failure and no relapse after achieving SVR₁₂ (defined as any SVR₂₄ non-responder who prematurely discontinued study drug [study drug duration < 52 days for subjects assigned to 8 weeks of treatment, and < 105 days for subjects assigned to 16 weeks of treatment] and did not meet the **On-treatment HCV virologic failure or Relapse₂₄** definitions);
5. HCV reinfection (see definition described earlier);

6. Missing follow-up data in the SVR₂₄ window (defined as any subject who completed study drug without data in the SVR₂₄ window after applying the imputation rules and not meeting the definitions of [1], [2], [3], [4], or [5]);
7. Other (defined as any SVR₂₄ non-responder not meeting the definitions of [1] – [6]).

For the reasons for SVR₁₂ and SVR₂₄ nonresponse defined above, subjects are only to be counted in 1 category. For example, the categories of premature discontinuation and reinfection are mutually exclusive. Thus, subjects who are SVR₁₂ or SVR₂₄ nonresponders meeting the definition of HCV reinfection will be counted in the reinfection category and will not be counted in any other category (as in the example, even if such a subject appears to meet the definition of prematurely discontinued study drug with no on-treatment HCV virologic failure, the subject would be counted in the reinfection category only).

10.2 Handling of Multiplicity

In order to control the Type I error rate at 0.05, a fixed sequence testing procedure⁷ will be used for the ranked primary efficacy endpoints. That is, only if success has been demonstrated for the first primary endpoint will the testing proceed to the second primary endpoint. Similarly, only if success has been demonstrated for the second primary endpoint will the testing proceed to the third primary endpoint.

10.3 Primary Efficacy Analysis

The primary efficacy endpoint is the percentage of Arm A subjects achieving SVR₁₂. The three ranked primary efficacy endpoints are:

1. The percentage of Arm A subjects from the combined group of GT1 to 6-infected subjects in the ITT population achieving SVR₁₂. The percentage of these subjects with SVR₁₂ will be non-inferior to the historical SVR₁₂ rate of 96% if the lower confidence bound (LCB) of the 2-sided 95% CI for the percentage is > 90%.

2. The percentage of Arm A subjects from the group of GT1-infected subjects in the ITT population achieving SVR₁₂. The percentage of these subjects with SVR₁₂ will be non-inferior to the historical SVR₁₂ rate of 97% if the LCB of the 2-sided 95% CI for the percentage is > 91%.
3. The percentage of Arm A subjects from the group of GT2-infected subjects in the ITT population achieving SVR₁₂. The percentage of these subjects with SVR₁₂ will be non-inferior to the historical SVR₁₂ rate of 95% if the LCB of the 2-sided 95% CI for the percentage is > 89%.

The normal approximation to the binomial distribution will be used to calculate each CI unless the rate for the primary endpoint is 100%, in which case the Wilson's score method will be used for the calculation of the CI.⁸

10.4 Secondary Efficacy Analyses

The secondary efficacy endpoints are:

- the percentage of Arm A subjects with on-treatment HCV virologic failure (defined as **On-treatment HCV virologic failure**);
- the percentage of Arm A subjects with post-treatment relapse (defined as **Relapse**₁₂; subjects with reinfection will be summarized separately);
- the percentage of Arm A HCV/HIV co-infected subjects (determined at Screening) achieving SVR₁₂.

The numbers and percentages of subjects with on-treatment HCV virologic failure, post-treatment relapse (**Relapse**₁₂), and SVR₁₂ will be calculated along with two-sided 95% Wilson score CIs.⁸

In addition, a summary of reason for SVR₁₂ non-response (e.g., on-treatment HCV virologic failure, relapse, re-infection, other) will be provided for the set of all Arm A subjects and for the set of HCV/HIV co-infected Arm A subjects. Listings of subject numbers with reason for non-response will be prepared.

The secondary endpoints will be summarized for the set of all Arm A subjects in the ITT population and for the Arm A subjects in each of the GT1-infected and GT2-infected groups.

10.5 Sensitivity Analyses for SVR₁₂

Two-sided 95% CIs for the SVR₁₂ rates of the primary endpoints will be calculated using both the normal approximation to the binomial distribution and the Wilson score method.⁸

The analyses of the primary endpoints will also be performed on Arm A of the mITT-GT and mITT-GT-VF populations. Both two-sided 95% normal approximation and Wilson score CIs will be provided for each of these sensitivity analyses.

The analyses described above will also be performed for the geographic region of China within the overall set of Arm A subjects and the Arm A subjects in each of the GT1-infected and GT2-infected groups for the populations specified above.

The number and percentage of subjects with SVR₁₂ and the corresponding 95% Wilson score CI will be provided for each randomization stratum:

- China/GT1-infected/HIV co-infected
- China/GT1-infected/non-HIV co-infected
- China/GT2-infected/HIV co-infected
- China/GT2-infected/non-HIV co-infected
- China/GT3 – 6-infected/HIV co-infected
- China/GT3 – 6-infected/non-HIV co-infected
- Singapore/GT1-infected/HIV co-infected
- Singapore/GT1-infected/non-HIV co-infected
- Singapore/GT2-infected/HIV co-infected
- Singapore/GT2-infected/non-HIV co-infected
- South Korea/GT1-infected/HIV co-infected
- South Korea/GT1-infected/non-HIV co-infected

- South Korea/GT2-infected/HIV co-infected
- South Korea/GT2-infected/non-HIV co-infected

For each sensitivity analysis, a two-sided 95% CI will be produced only if there are at least 10 subjects in the summary.

Listings of subjects excluded from the mITT-GT and mITT-GT-VF populations will be provided, as applicable.

10.5.1 Imputation Approaches

In addition to imputing SVR₁₂ as described in Section 6.3, SVR₁₂ will be presented for the overall set of Arm A subjects and the Arm A subjects in each of the GT1-infected and GT2-infected groups in the ITT population using the following other methods to impute missing HCV RNA values:

- impute any missing HCV RNA values in the SVR₁₂ window by carrying forward the last non-missing (post-baseline) HCV RNA value prior to the SVR₁₂ window;
- impute as described in Section 6.3 but treat SVR₁₂ non-responders who were categorized as "prematurely discontinued study drug with no on-treatment virologic failure" or "missing follow-up data in the SVR₁₂ window" as successes.

For each of these, the number and percentage of Arm A subjects with SVR₁₂ will be presented along with two-sided 95% CIs using both the normal approximation to the binomial distribution and the Wilson score method. Within the 3 groups of subjects specified above, these analyses will also be performed for the geographic region of China.

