5.1.2 Modified Intention-to-Treat (mITT) Populations

Sensitivity analyses of SVR₁₂ as described in Section 10.5, when applicable, will be performed on the ITT population modified to exclude subjects who have multiple GTs according to the central laboratory or phylogenetic analyses of the baseline sample or subjects who received an incorrect duration of treatment due to incorrect classification of

GT or treatment experience at randomization (mITT-GT), and on the mITT-GT population modified to exclude subjects who did not achieve SVR₁₂ for reasons other than virologic failure (i.e., subjects with reasons other than on-treatment HCV virologic failure and relapse) (mITT-GT-VF).

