- The percentage of subjects who relapsed after achieving SVR₁₂ (**Relapse₂₄**).

* These endpoints will be summarized for the HCV/HIV co-infected subjects (determined at Screening) within the populations/groups identified above.

In the above analyses for SVR, HCV virologic failure, and relapse, the number and percentage of subjects with each endpoint among those receiving active treatment during the DB or the OL Treatment Period, as applicable, will be calculated along with a two-sided 95% Wilson score CI. Imputations for missing data will be performed as described in Section 6.3 for analysis of SVR, HCV virologic failure, and relapse. All other endpoints will be presented using data as observed.

As additional endpoints, the secondary endpoints will be summarized for the geographic region of China within the set of Arm A subjects in the ITT population and in each of the GT1-infected and GT2-infected groups of the ITT population.

A summary of the subjects who completed treatment and relapsed (defined as **Relapse_{overall}**) will be prepared displaying the number of subjects relapsing overall and by SVR visit window (within the SVR₄, SVR₁₂, SVR₂₄ windows or after SVR₂₄ window), including the subject number and the SVR visit window corresponding to the first HCV RNA value of those indicating the occurrence of relapse. A similar listing will be prepared for subjects who prematurely discontinued treatment and relapsed after having HCV RNA < LLOQ at their Final Treatment Visit. These summaries will be presented across geographic regions and for the geographic region of China within the set of Arm A

subjects in the ITT population and in each of the GT1-infected and GT2-infected groups of the ITT population as well as within the overall OL population and the GT1-infected and GT2-infected groups in the OL population.

Listings of subject numbers with reason for non-response will be prepared for the SVR endpoints.

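### The success-imputation sensitivity analysis in SAP 10.5.1 also recodes early stoppers with measured post-treatment viraemia as SVR12 successes, and mITT-GT-VF leaves the same subjects out

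*SAP*

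**What the plan says.** SAP 10.5.1 presents SVR12 "using the following other methods to impute missing HCV RNA values". The first method carries the last value forward. The second follows SAP 6.3 but then counts as successes the SVR12 "non-responders who were categorized as 'prematurely discontinued study drug with no on-treatment virologic failure' or 'missing follow-up data" in the SVR12 window.

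Those categories come from the list of reasons for SVR12 non-response in SAP 10.1:

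- Reason 3 is "defined as any SVR₁₂ non-responder who prematurely discontinued study drug" before 52 days (8-week assignment) or 105 days (16-week assignment) without meeting the on-treatment virologic failure definition. It sets no condition on whether HCV RNA was measured.
- Reason 5, missing follow-up data, covers only subjects who completed study drug and have no value in the window after imputation.
- Relapse12 applies "for a subject with HCV RNA < LLOQ at Final Treatment Visit who completed treatment and has post-treatment HCV RNA data available", and "completion of treatment is defined as a study drug duration of 52 days or greater for subjects assigned to 8 weeks of treatment".
- End-of-treatment failure needs at least 36 days of drug and a sample on or after Day 36.

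SAP 5.1.2 forms mITT-GT-VF by removing from mITT-GT the subjects without SVR12 "for reasons other than virologic failure (i.e., subjects with reasons other than on-treatment HCV virologic failure and relapse". SAP 10.7 plans a separate listing of "subjects who prematurely discontinued treatment and relapsed after having HCV RNA < LLOQ at their Final Treatment Visit". SAP 10.8 plans sequencing for reason-3 non-responders (all from South Korea and Singapore, GT1 from China) who have HCV RNA of at least 1000 IU/mL after stopping.

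**The concern.** A best-case analysis for missing data should vary only outcomes that were not observed. This rule works on whole non-response categories, and one of them can contain observed failures. A subject with measured virus after stopping would be reported as cured. SAP 10.7 and 10.8 show that the plan expects such subjects.

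mITT-GT-VF treats the same subjects as having failed for a non-virologic reason. That population also feeds the logistic regression in SAP 10.6 and the baseline-polymorphism comparisons in SAP 10.8, where losing a true rebound could mask an association. What is at stake is how far these supporting analyses can be trusted. The confirmatory tests are not at stake.

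**Working it through.** **1. Who falls into reason 3 (SAP 10.1)**

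| Early stopper without SVR12 | Classified as | Second method in 10.5.1 | mITT-GT-VF |
|---|---|---|---|
| Breakthrough, or end-of-treatment failure (Day 36 or later) | On-treatment failure | stays failure | kept |
| Reinfection | Reinfection only | stays failure | excluded |
| Below LLOQ at final treatment visit, then quantifiable | Reason 3 | **success** | excluded |
| Stopped before Day 36 still viraemic, no breakthrough | Reason 3 | **success** | excluded |
| No HCV RNA in the SVR12 window, last value below LLOQ | Reason 3 | success | excluded |

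Only the last row is plainly a missing-data case. The third row shows the discontinuity: for an 8-week subject, the same rebound is Relapse12 after 52 days of drug and a success after 51.

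**2. Reading the plan's inputs correctly**

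SAP 4.3 gives Arm A sizes of 336, 170 and 126, assumed rates of 97%, 97% and 96%, and thresholds of 90%, 91% and 89%. Power is Φ{[(p1 − p0) − 1.96·√(p0(1 − p0)/n)] / √(p1(1 − p1)/n)}.

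- GT1: (0.06 − 1.96 × 0.02195)/0.01308 = 1.30, power 90.3% (stated 90%).
- GT2: (0.07 − 1.96 × 0.02787)/0.01746 = 0.88, power 81.1% (stated above 80%).
- Overall: above 99.9% (stated above 95%).

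All three reproduce.

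**3. Effect of one recoded subject**

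The rate rises by 1/336 = 0.30, 1/170 = 0.59 or 1/126 = 0.79 points. In the China analyses (SAP 10.5 and 10.5.1), with about 100 Arm A subjects in each of GT1 and GT2 (SAP Table 1), it is 1.0 point.

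The lower bound is p − 1.96·√(p(1 − p)/n). Suppose the ITT result just misses and one failure is a viraemic reason-3 subject (an illustration; the counts are assumed):

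| Group (threshold) | ITT | Second method, 10.5.1 | mITT-GT-VF |
|---|---|---|---|
| Overall (90%) | 311/336: 89.75% | 312/336: 90.10% | 311/335: 90.07% |
| GT1 (91%) | 160/170: 90.58% | 161/170: 91.34% | 160/169: 91.29% |
| GT2 (89%) | 117/126: 88.36% | 118/126: 89.39% | 117/125: 89.31% |

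For GT2: 0.92857 − 1.96 × 0.02294 = 0.8836, and 0.93651 − 1.96 × 0.02172 = 0.8939. With 1 to 5 such subjects the GT2 bound runs from 89.39% to 93.76% under the recode and from 89.31% to 93.51% in mITT-GT-VF. With the Wilson interval, which 10.5.1 also reports, three recoded subjects are needed in every group (90.29%, 91.75% and 90.00%).

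**4. How likely is a result near the threshold?**

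The normal-approximation rule tolerates at most 24, 9 and 8 failures. At the planned rates about 336 × 0.03 = 10.1, 170 × 0.03 = 5.1 and 126 × 0.04 = 5.0 are expected.

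**5. How many subjects could be affected?**

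The documents give no figure. Protocol Table 5 gives a rough ceiling from 8-week, non-cirrhotic, non-GT3 subjects:

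- SVR12 in 383 + 193 + 43 + 2 + 9 = 630 of 387 + 197 + 46 + 2 + 10 = 642, so 12 non-responders.
- One on-treatment failure and two relapses leave 9 with other reasons: 9/642 = 1.4%, or about 5 of 336.
- GT2: 4 non-responders less 2 relapses leaves 2/197 = 1.0%, or about 1 of 126.

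Viraemic early stoppers can only be some of these. This assumes the earlier studies classified reasons in a similar way.

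**The case against.** The strongest reply is that nothing confirmatory depends on this. The primary analysis is ITT with missing counted as failure (SAP 6.3 and 10.3), the fixed sequence runs on those endpoints, and no sensitivity result can reverse them. Carrying the last value forward fills only missing values, so measured viraemia stays a failure there. All of this stands.

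The affected subjects are also disclosed, through reasons for non-response with listings (SAP 10.4), listings of mITT-GT-VF exclusions (SAP 10.5) and the listing in SAP 10.7. That stands too, but a listing does not correct a rate that counts them as cured.

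SAP 12.1 says the imputation approaches were added to align with the development program. That explains where the rule came from; it does not justify calling it imputation of missing values. Limiting relapse to completers is a defensible choice, and both it and mITT-GT-VF are set in the protocol (8.1 and 8.1.2.2). This is a good reason not to redefine that population.

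A reader might infer more than the documents support:

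- That every early-discontinuation non-responder becomes a success. On-treatment failures, including subjects stopped under the virologic criteria of Protocol 5.4.1.1, and reinfections do not.
- That mITT-GT-VF is a missing-data analysis. Neither document presents it as one.
- That an assumed early-stop rate of, say, 1 to 3% of 336 (3 to 10 subjects) gives the number wrongly recoded. It counts all early stoppers, including those who reach SVR12 and those with no observed viraemia.
- That the planned sensitivity analyses cannot support the primary result at all. The recode fails to isolate missing data only if viraemic early stoppers occur.

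**Conclusion.** The point holds in limited form. As written, the second method in SAP 10.5.1 turns some observed virologic failures into successes, and mITT-GT-VF drops the same subjects as non-virologic. Both can only move SVR12 upward relative to counting these subjects as failures. The bias is confined to that sensitivity analysis and to the analyses that use mITT-GT-VF (SAP 10.5, 10.6 and 10.8).

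The size is 0.30, 0.59 or 0.79 points per subject (overall, GT1, GT2). One subject can change a sensitivity conclusion, but only when the ITT result sits just below its threshold, which is not expected at the planned rates. The conclusion about the rule rests on the SAP definitions alone. The threshold examples rest on assumed counts, and the view that few subjects are involved rests on Protocol Table 5 carrying over to this trial. The rule should be corrected because it does something other than what it is said to do.

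**What to change.** In the second method of SAP 10.5.1, count non-responders with reason 3 or reason 5 as successes only if all three conditions hold:

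1. no HCV RNA value exists in the SVR12 window after the SAP 6.3 imputation;
2. no post-treatment HCV RNA is at or above LLOQ;
3. the last available HCV RNA value is below LLOQ.

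Everyone else stays a failure. The third condition is needed for a subject who stops before Day 36 without ever being suppressed and is then lost, who has no post-treatment value to test.

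Leave the protocol-defined mITT-GT-VF as it is, and add a version that retains, as virologic failures, early discontinuers with quantifiable post-treatment HCV RNA, excluding reinfection.

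The cost is one extra condition and one extra run, with no new data. The sensitivity rates may come out slightly lower.
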